10.1.3 Changes in risks c.f. standard cardioversion procedure in placebo group

- Groin access complications (<0.2% with ultrasound guidance)

- Electrophysiologist administering cardioversion in catheter lab environment (potentially better safety monitoring than in standard cardioversion environment)

11. Statistical considerations

11.1 Sample size

The sample size of 20 subjects for the pilot study has been chosen as an achievable recruitment target that would enable assessment of feasibility of the study, and to confirm whether a larger trial could be conducted.

The sample size for the larger trial is calculated based on the comparison of recurrence free survival in the two groups using the logrank test. The expected percentage of patients with recurrence of AF within one year is 47% for the ablation group¹ and 66% for DCCV^{2,3,4} based on published data. This is equivalent to a hazard ratio of 1.7. To detect an effect of this size with 80% power at the 5% significance level would require N=104 patients in each group.

For secondary endpoints the sample size of 104 patients will give 80% power at the 5% significance level to detect an effect size of 0.4 standard deviations in any continuous variable.

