6.1 Primary objective

The primary hypothesis being tested is that 20 patients undergoing pulmonary vein isolation with cryoablation with DCCV for atrial fibrillation will have lower rates of AF recurrence than those treated by DC cardioversion without an ablation procedure.

Once funding is available and dependent on the results of the pilot, it is planned that the study will be extended to a larger trial following an amendment to the REC, to increase the recruitment target to 208 participants and involve 4-5 other UK centres.

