9.3 Procedure protocol

9.3.1 All patients

Patient gives informed consent in pre-admission. Patients will be blinded to their ECG and rhythm. Admitted to day ward. Arrival in Lab and checked in as for Cryo PVI. Skin electrodes placed. Conscious sedation or GA administered and sterile field prepared. 8F and 7F sheaths placed in RFV under ultrasound guidance. Heparin given as per local AF ablation protocol.

Once sheaths in place and GCS < 10, randomisation will be performed via REDCap, a web-based, electronic database. Patients will be randomised in a 1:1 ratio to either DCCV+ PVI or DCCV alone.

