11.2 Method of analysis

The statistical analysis plan (SAP) will describe the statistical methods which will be used in the analysis of data, including any interim analyses and the level of significance that is to be used.

Progression criteria

This study has been designed with an internal pilot phase aimed at assessing the feasibility and optimizing the methods to be used in the main study, piloting key study logistics, improving quality and efficient use of resources. Eldridge (Eldridge et al., 2016) have described a new framework where 'internal pilot' studies which have some feasibility objectives but focus on the processes to be used in the main study generating data which can contribute to the final analyses. They describe the use of operational 'progression criteria' which can be used to measure pre-identified targets at the end of the pilot phase which will determine whether or not to proceed to the main trial. This approach has been advocated by the members of the Internal Pilot Trials Workshop supported by the Hubs for Trials Methodology Research (Avery et al., 2017). Avery and colleagues describe some of the key issues to consider in development and review of these criteria.

In the current study the following progression criteria have been identified to assess operational aspects of the design and progression to the main trial:

- Protocol non-adherence – (a) cross-over from DCCV to AF ablation group. Estimate 25-30% as in CABANA trial (Packer et al., 2018). We will take this level of cross-over into account in our power calculations. (b) Measure the amount of off protocol intervention.

- Recruitment rate – we estimate being able to recruit 4 patients per month. If the number falls below this we will need to build this into timelines for the larger trial.
- Loss to follow-up. Estimate 2%.
- Key study logistics – especially around the delivery of the intervention, including the use of a 'chaperone' to maintain blinding.
- Identifying barriers and facilitators to implementation.
- Assessment of the success of the blinding procedure (ie. blinding index).
- Assessment of the feasibility of the blinding SOP.
- Assessment of the acceptability of the interventions
- Data collection – completeness and quality. How much missing data are we willing to tolerate?
- Assessment of outcome measures.

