The TSC will discuss and evaluate the progression criteria at the end of the Pilot phase and use a Red Amber Green (RAG) system to decide which operational aspects of the design need to be changed before proceeding to the main trial.

12. Ethics

The Principal Investigator will ensure that the study will be carried out in accordance with the ethical principles in the UK Policy Framework for Health and Social Care Research (Nov 2017), and applicable legal and regulatory requirements. This protocol and any subsequent amendments, along with any accompanying material provided to the patient in addition to any advertising material will be submitted by the Investigator to an independent NHS Research Ethics Committee (REC). Written Approval from the Committee must be obtained and subsequently submitted to the JRMO to obtain Final Sponsorship approval.

12.1 Risks of the procedures:

All patients having either a DCCV or AF ablation are given conscious sedation or general anaesthetic.

An AF ablation is performed using transeptal puncture using standard techniques. The risks associated with a transeptal puncture are very low. Groin access complications are around 1% and even less with ultrasound guidance (0.2%).

The DCCV only group would require the patients to have a line put in, which is not normally done. However, this venous access could be used for the administration of anaesthetic agents, sedation and fluids. The use of a femoral venous access will allow patients to be blinded to which procedure they have received and enable the specific effects of the AF ablation to be measured.

Any risks associated with femoral access will have been minimised by using ultrasound guidance for the venous access. The risks of the ablation procedure also need to be balanced against the risks associated with the patient being maintained on medications to reduce their risk of arrhythmia.

12.2 Informed consent:

The risks to the study participants will be adequately explained in the Patient Information Sheet and Informed Consent Form.

The patients will be considered suitable to have either a cardioversion or ablation procedure. So, they need to be willing to have the transeptal puncture for the AF ablation. The risks of this procedure are low (as detailed above). As the procedure is performed under anaesthetic it will be performed without the patient experiencing any pain.

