12.3.1 Rationale for blinding

The rationale for blinding where possible in clinical trials is well established, and discussed in Introduction (Section 5.4).

Placebo effects and distorted participant reporting appear to be greater in surgical trials than in drug trials. There are many factors involved in surgical procedures such as hospitalization, ancillary treatments, the surgical ritual itself or the technology used that can all heighten the placebo effect. Correcting for placebo effects is becoming more important as more subjective 'soft' outcome measures are used eg. Quality of Life (which are more prone to be influenced by placebos).

The magnitude of the placebo effect may be a critical factor in determining the outcome of a trial. A difference between two treatments such as DCCV and PVI might result from differences in their placebo effects so it is important to blind patients to the intervention they have received.

Specific emphasis will be placed on this being a blinded trial. Patients will be informed that they may receive an electrical cardioversion with or without pulmonary vein isolation procedure. The procedure performed will be determined at random following administration of sedation and insertion of groin sheaths under ultrasound guidance. Patients will not be informed which procedure they have undergone until the end of the trial period or the study end-point whichever is sooner. Patients who undergo a cardioversion only who revert to persistent AF will be offered a pulmonary vein isolation procedure if indicated as standard medical care under current guidelines.

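### The main-trial size of 104 per arm is correctly computed but does not yet allow for the crossover and loss that Protocol 11.2 expects, and the SAP counts crossover only at the index procedure

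*Protocol*

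**What the plan says.** Protocol 11.1 and the synopsis size the main trial on a log-rank comparison, with one-year recurrence of 47% after ablation and 66% after DCCV, a hazard ratio of 1.7, 80% power and 5% significance: "To detect an effect of this size with 80% power at the 5% significance level would require N=104 patients in each group". The total is 208. Neither place mentions crossover, loss to follow-up or section 11.2.

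The progression criteria in Protocol 11.2 begin with crossover from DCCV to ablation, estimated at 25-30%, and add: "We will take this level of cross-over into account in our power calculations". They put loss to follow-up at 2%. The steering committee is to use these criteria to "decide which operational aspects of the design need to be changed before proceeding to the main trial". Section 6.1 makes the extension conditional: "dependent on the results of the pilot, it is planned that the study will be extended to a larger trial".

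On the route to ablation in the DCCV arm, Protocol 12.3.1 says: "Patients who undergo a cardioversion only who revert to persistent AF will be offered a pulmonary vein isolation procedure", if indicated. Patients are not told their allocation "until the end of the trial period or the study end-point whichever is sooner".

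SAP 6.4.4 defines non-adherence as receiving the other arm's treatment during the index procedure, and Table 2 has a row for the proportion crossing over. On the timing of randomisation, Protocol 9.3.1 says: "Once sheaths in place and GCS < 10, randomisation will be performed via REDCap". Later AF procedures of any kind form a single secondary endpoint in SAP 6.4.5, reported in Table 4.

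**The concern.** The only sample size printed for the primary endpoint rests on no crossover and no loss, while the next section of the protocol expects both. The stated 80% therefore holds only under conditions that the plan's own estimates put in doubt, and a reader of 11.1 or the synopsis is not told so.

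If the adjustment is meant to follow the pilot, the pilot has to supply a usable crossover figure. As defined, it will not. Allocation is revealed to a team with the patient already sedated and sheathed, and the allocated procedure follows at once. Crossover at that point can be little more than operator non-adherence. The route to ablation that the protocol describes comes later and is not counted as crossover. The steering committee could see a figure near zero under the first progression criterion and leave 208 unchanged, without knowing how often DCCV patients received PVI or whether this came before their primary event.

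**Working it through.** **Inputs.** Recurrence 0.47 and 0.66, 80% power, 5% significance (Protocol 11.1); 1:1 allocation (9.3.1); crossover 25-30% and loss 2% (11.2). Assumed here: a two-sided test, constant hazards, and crossovers taking the ablation-arm hazard.

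**1. Reproduce 104.**
- HR = ln(0.34)/ln(0.53) = 1.699.
- Freedman events = (1.960 + 0.842)² × ((HR + 1)/(HR − 1))² = 7.849 × (2.699/0.699)² = 117.0.
- Per arm = 117.0/(0.47 + 0.66) = 103.5, so 104.
- Power at 104: events = 104 × 1.13 = 117.5; Φ(√117.5 × 0.699/2.699 − 1.960) = 80.2%.

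The match is exact with no inflation term. Other formulas fit less well: Schoenfeld gives 100 per arm, two proportions 106, and one-sided Freedman 83.

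**2. Loss of 2% alone.** Events = 117.5 × 0.98 = 115.2, so power is 79.4%. Restoring 80% takes 103.5/0.98 = 105.6, so 106 per arm (107 if 104 is used as the base).

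**3. Crossover only after a counted recurrence.** Time to first recurrence is unaffected, so power stays at 80.2%, or 79.4% with loss.

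**4. Crossover from time 0 (illustrative worst case).** A random fraction c of the DCCV arm has the ablation-arm risk throughout: p = 0.66 − 0.19c and HR = ln(1 − p)/ln(0.53).

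| c | p | HR | Power at 104 | With 2% loss | Per arm for 80% |
|---|---|---|---|---|---|
| 0.25 | 0.6125 | 1.493 | 55.5% | 54.7% | 186 |
| 0.30 | 0.603 | 1.455 | 49.9% | 49.1% | 213 |

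**5. Crossover part-way, while recurrence-free.** Of a random fraction c, those still free of recurrence at time t (in years) move to the ablation hazard: p = (1 − c) × 0.66 + c × [1 − exp(−1.079t − 0.635(1 − t))], where 1.079 = −ln 0.34 and 0.635 = −ln 0.53. The average hazard ratio goes into the same formula, so the results are approximate.
- t = 3 months: power 63.5% (c = 0.25) or 59.7% (c = 0.30).
- t = 6 months: power 70.3% or 68.0%.

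**6. Which timing do the documents describe?** Protocol 12.3.1 offers PVI after reversion to persistent AF. Protocol 6.3 makes recurrence of persistent AF the primary event. PVI by that route, after the 6-week blanking period, therefore follows the event (step 3). Inside the blanking period a reversion is not counted (SAP 6.4.5), so PVI then would precede any counted event. The documents give no frequency for this.

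**7. What the pilot will report.** Table 2 reports crossover at the index procedure only. Table 4 pools later PVI with repeat DCCV. Table 2 also has an off-protocol deviation row, but it is undefined, and PVI offered under 12.3.1 is arguably within protocol. No row gives PVI in the DCCV arm over 12 months.

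**8. Precision.** With about 10 DCCV patients, the exact 95% interval for 0/10 is 0 to 1 − 0.025^(1/10) = 30.8%. For 3/10 it is 6.7% to 65.2%.

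**The case against.** The best reply is that the adjustment is deferred, not forgotten. The sentence in 11.2 is in the future tense and sits among the progression criteria. The 208 is a planning target that depends on funding, the pilot results and an ethics amendment, with steering committee review first. That stands: a reader might infer that 208 is a miscalculation or that the protocol has broken its own commitment, and the documents support neither.

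Second, the main described route to PVI follows the primary event and so costs no power. This also stands. A reader might infer from step 4 that the main trial has only 50-56% power. The documents do not support that as an expectation, because randomisation under sedation leaves little room for crossover at time 0. Those figures are an outer bound.

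A reader might also model re-treatment of early reverters during the blanking period in the DCCV arm alone and obtain a severe loss. Patients and treating clinicians are blinded, and allocation stays concealed until the trial end or the end-point, so the documents give no clear mechanism for re-treating one arm only. That calculation should not be used.

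Third, 2% loss costs under one point of power, and replacement of withdrawn patients (Protocol 9.10) may offset part of it. Agreed.

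Fourth, later procedures are recorded, and ten patients can barely test a 25-30% assumption. Both are true. They make the fix a matter of tabulation and call for an interval; they do not make an index-only count informative. Whether the 25-30% taken from the cited trial refers to index or later crossover cannot be seen from the documents, so comparability is uncertain either way.

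**Conclusion.** The concern holds as an assumption not yet carried through. The 104 per arm is arithmetically correct for no crossover before the primary event and no loss, and the printed text does not say so. With PVI only after a counted recurrence, power is about 80%, or 79% with 2% loss. With PVI before the event it is lower, by an amount set by timing that the documents do not give; 56% and 50% bound this at 25% and 30% crossover from time 0, under constant hazards and full uptake of the ablation-arm risk.

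Separately, the index-only definition in SAP 6.4.4 should give a pilot crossover figure near zero and will miss the later route to ablation that the protocol itself describes. The missing allowance and the narrow definition are certain; the size of the effect on power is not. The pilot does no hypothesis testing (SAP 6.5), and none of its planned analyses is affected. This should be fixed before the decision on the main trial.

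**What to change.** 1. **Protocol 11.1 and synopsis.** State that 104 per arm gives 80% power for the primary endpoint only with no crossover before the primary event and no loss. Cross-refer to 11.2, and say that 208 will be re-examined for crossover before the main trial. Give the power range at 25% and 30% crossover with its timing assumptions, labelled illustrative.
2. **SAP 6.4.4 and Table 2.** Keep index non-adherence. Add a row for PVI in the DCCV arm at any time to 12 months, split into before and after the first countable primary event, with an exact confidence interval.

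The cost is a few sentences in the protocol and one table row with its definition, using repeat-procedure and loop-recorder data already being collected. The stated power becomes conditional and looks less favourable. No pilot analysis, pilot sample size or clinical rule changes.

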11.2 Method of analysis

The statistical analysis plan (SAP) will describe the statistical methods which will be used in the analysis of data, including any interim analyses and the level of significance that is to be used.

Progression criteria

This study has been designed with an internal pilot phase aimed at assessing the feasibility and optimizing the methods to be used in the main study, piloting key study logistics, improving quality and efficient use of resources. Eldridge (Eldridge et al., 2016) have described a new framework where 'internal pilot' studies which have some feasibility objectives but focus on the processes to be used in the main study generating data which can contribute to the final analyses. They describe the use of operational 'progression criteria' which can be used to measure pre-identified targets at the end of the pilot phase which will determine whether or not to proceed to the main trial. This approach has been advocated by the members of the Internal Pilot Trials Workshop supported by the Hubs for Trials Methodology Research (Avery et al., 2017). Avery and colleagues describe some of the key issues to consider in development and review of these criteria.

In the current study the following progression criteria have been identified to assess operational aspects of the design and progression to the main trial:

- Protocol non-adherence – (a) cross-over from DCCV to AF ablation group. Estimate 25-30% as in CABANA trial (Packer et al., 2018). We will take this level of cross-over into account in our power calculations. (b) Measure the amount of off protocol intervention.

- Recruitment rate – we estimate being able to recruit 4 patients per month. If the number falls below this we will need to build this into timelines for the larger trial.
- Loss to follow-up. Estimate 2%.
- Key study logistics – especially around the delivery of the intervention, including the use of a 'chaperone' to maintain blinding.
- Identifying barriers and facilitators to implementation.
- Assessment of the success of the blinding procedure (ie. blinding index).
- Assessment of the feasibility of the blinding SOP.
- Assessment of the acceptability of the interventions
- Data collection – completeness and quality. How much missing data are we willing to tolerate?
- Assessment of outcome measures.

The TSC will discuss and evaluate the progression criteria at the end of the Pilot phase and use a Red Amber Green (RAG) system to decide which operational aspects of the design need to be changed before proceeding to the main trial.

12. Ethics

The Principal Investigator will ensure that the study will be carried out in accordance with the ethical principles in the UK Policy Framework for Health and Social Care Research (Nov 2017), and applicable legal and regulatory requirements. This protocol and any subsequent amendments, along with any accompanying material provided to the patient in addition to any advertising material will be submitted by the Investigator to an independent NHS Research Ethics Committee (REC). Written Approval from the Committee must be obtained and subsequently submitted to the JRMO to obtain Final Sponsorship approval.

12.1 Risks of the procedures:

All patients having either a DCCV or AF ablation are given conscious sedation or general anaesthetic.

An AF ablation is performed using transeptal puncture using standard techniques. The risks associated with a transeptal puncture are very low. Groin access complications are around 1% and even less with ultrasound guidance (0.2%).

The DCCV only group would require the patients to have a line put in, which is not normally done. However, this venous access could be used for the administration of anaesthetic agents, sedation and fluids. The use of a femoral venous access will allow patients to be blinded to which procedure they have received and enable the specific effects of the AF ablation to be measured.

Any risks associated with femoral access will have been minimised by using ultrasound guidance for the venous access. The risks of the ablation procedure also need to be balanced against the risks associated with the patient being maintained on medications to reduce their risk of arrhythmia.

12.2 Informed consent:

The risks to the study participants will be adequately explained in the Patient Information Sheet and Informed Consent Form.

The patients will be considered suitable to have either a cardioversion or ablation procedure. So, they need to be willing to have the transeptal puncture for the AF ablation. The risks of this procedure are low (as detailed above). As the procedure is performed under anaesthetic it will be performed without the patient experiencing any pain.

There is a benefit to participants in the study in having the implantable cardiac device which will monitor their heart allowing immediate knowledge if their heart rhythm goes back into AF. Otherwise there are no further individual benefits in participating in the study.

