Objectives / aims	
The main aim of the research is to investigate whether patients undergoing pulmonary vein isolation with cryoablation for atrial fibrillation (AF) will have lower rates of AF recurrence than those treated by DC cardioversion without an ablation procedure.
 
The objectives of the Pilot Study are to trial the key study logistics with a view to optimising methods to be used in the main study.

Number of participants	20 patients (10 per group) for the pilot study 208 patients for the larger trial
Inclusion and exclusion criteria	
Inclusion criteria :
 
Persistent AF (atrial fibrillation lasting > 7days) of total continuous duration <2 years, Age 18-80, ability to give informed consent.
 
Exclusion criteria :
 
Creatinine clearance (eGFR) < 30mls/min, contraindication or unable to take anticoagulation, uncontrolled hypertension, contraindication or catheter ablation, BMI > 35. Contraindication or unable to tolerate amiodarone.

Statistical methodology and analysis (if applicable)	
The sample size for a pilot study is based on 10% of the sample size of the full trial. The sample size for the full trial is calculated based on the comparison of recurrence free survival in the two groups using the logrank test. The expected percentage of patients with recurrence of AF within one year is 47% for the ablation group¹ (January et al., 2014) and 66% for DCCV^{2,3,4} (Heeringa et al., 2006; Jones, Pollit, Fitzmaurice, Cowan, & Guideline Development, 2014; Wilber et al., 2010) based on published data.
 
This is equivalent to a hazard ratio of 1.7. To detect an effect of this size with 80% power at the 5% significance level would require N=104 patients in each group.
 
For secondary endpoints the sample size of 104 patients will give 80% power at the 5% significance level to detect an effect size of 0.4 standard deviations in any continuous variable.
 
Secondary endpoints:
 
Results will be presented as the mean (SD), median (IQR) or percentage (number) in each group. Continuous variables will be compared between the two groups using Student's T test for normally distributed variables and Mann-Whitney U test for those with non-normal distributions. Categorical variables will be compared with Chi-squared tests.

Study duration	The Pilot study will take place at Barts Health NHS Trust : 4

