	
months to set up, 3 months to recruit, treatment (1 day), 3 month follow up and 2 months study closure. For the larger trial in 4-5 UK centres: Set-up 6 months, 6 month recruitment, treatment (1 day), 12 month follow-up, 3 months study closure.

--	---

5. Introduction

Patients with persistent atrial fibrillation undergoing catheter ablation are reported to have fewer symptoms and better quality of life than those undergoing DC cardioversion (DCCV) or optimal medical therapy. However, as yet this has not been subjected to a randomised, prospective, blinded clinical trial (January et al., 2014).

Atrial fibrillation (AF) is the commonest cardiac arrhythmia, with a prevalence of 5.5% (Heeringa et al., 2006). A major cause of the life-changing complication of stroke, AF is associated with severe symptoms, such as palpitations, shortness of breath, lethargy and a reduced quality of life. AF can be classified into paroxysmal, persistent or long-standing persistent. Paroxysmal AF refers to when episodes last less than 7 days before spontaneously termination, persistent AF implies episodes lasting greater than 7 days or requiring either electrical or pharmacological cardioversion, and longstanding persistent AF describes AF episodes lasting more than one year in duration trial (January et al., 2014).

Patients differ widely in the diversity and severity of their AF symptoms. Some 15-30% of patients with AF are asymptomatic. Data from implantable cardioverter-defibrillators (ICDs) and pacemakers have demonstrated that up to 70% of paroxysms of AF are asymptomatic. There is a need to clarify the relationship between patient reported symptoms and the arrhythmia itself. It is likely that both somatic and psychological factors contribute to this relationship. Patient perception or awareness of symptoms is often not a good discriminator of the severity of the arrhythmia. In the present study we will also collect information from patients on reported symptoms and effects on quality of life (both physical and mental), functional status and treatment satisfaction. We will be able to look at these and assess the correlations between reported symptoms and arrhythmia as captured by the LINQ device.

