6.4.4 Assessment of feasibility endpoints

Protocol non-adherence is defined as the proportion of patients in each randomised group who undergo the treatment that they were not randomised to as part of the index procedure, i.e. those randomised to DCCV only undergoing DCCV plus PVI, and those randomised to the DCCV plus PVI group who only undergo DCCV as part of the index trial procedure.

Recruitment rate will be defined as the total number of patients recruited divided by the number of months during which recruitment takes place.

Loss to follow-up will be defined as a) the number lost to follow-up at 12 months as a proportion of the number randomised. b) the number who do not consent to the collection of 5-year registry data as a proportion of the number randomised.

Data completeness will be defined as the number of subjects completing each assessment as a proportion of the total randomised. For this pilot study, analyses will be conducted on a complete case basis, and the level of missing data will be assessed to help inform as to best methods to use to handle potential missing data within a larger future trial.

Blinding index will be assessed as described by Bang et al (BI)². Patients and staff will be asked to guess the treatment allocation and will answer DCCV, DCCV+PCI, or don't know. The BI is scaled to an interval of -1 to 1 with 1 being complete lack of blinding, 0 being perfect blinding and -1 indicating opposite guessing.

Other feasibility endpoints including assessing study logistics, identifying barriers and facilitators to implementation, and assessing the acceptability of the interventions will be assessed qualitatively, and hence will not be described further in the SAP.

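### The recruitment benchmark of 4 patients per month does not match the 3-month pilot window or the 6-month main-trial window, so a pilot that meets it would prompt no revision of the timelines

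*Protocol*

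**What the plan says.** Protocol section 11.2 (Progression criteria) gives the benchmark: "we estimate being able to recruit 4 patients per month". The consequence follows at once: "If the number falls below this we will need to build this into timelines for the larger trial". No unit (per site or for the whole pilot) and no red, amber or green cut-off is attached.

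The protocol synopsis gives the sizes as "20 patients (10 per group) for the pilot study 208 patients for the larger trial". Its study-duration row gives the pilot 4 "months to set up, 3 months to recruit, treatment (1 day), 3 month follow up and 2 months study closure". It continues: "For the larger trial in 4-5 UK centres: Set-up 6 months, 6 month recruitment". Section 6.1 words the expansion differently, as an intention to "increase the recruitment target to 208 participants and involve 4-5 other UK centres", so the main trial could have 4-5 centres in all or 4-5 besides the pilot Trust. The pilot runs at two sites of one Trust.

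SAP section 6.4.4 fixes the measure: "Recruitment rate will be defined as the total number of patients recruited divided by the number of months during which recruitment takes place". SAP section 6.1 adds that pilot patients will count in the main trial if that trial proves feasible and the design has not changed materially. The SAP gives no recruitment threshold of its own.

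**The concern.** Recruitment rate is one of the feasibility endpoints the pilot exists to measure, and 4 per month is the only figure in either document against which it can be read. A benchmark for timelines should be the rate at which those timelines hold. Here it appears to be set lower. If so, the pilot could meet its benchmark, no revision would be prompted, and the main trial would be planned, costed and opened on a recruitment period that the observed rate cannot support.

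**Working it through.** **Is the target of 208 itself sound?** Inputs from protocol section 11.1: one-year recurrence 47% and 66%, hazard ratio 1.7, 80% power, 5% significance (taken as two-sided), 1:1 allocation.

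- Hazard ratio: ln(1 − 0.66) / ln(1 − 0.47) = 1.699, which agrees with 1.7.
- Events (Freedman): (1.960 + 0.842)² × (2.7 / 0.7)² = 116.8, rounded up to 117.
- Patients: 117 / [(0.47 + 0.66) / 2] = 117 / 0.565 = 207.1, so 104 per group and 208 in all.

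The plan's figure reproduces, so 208 can be used as the recruitment target.

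**Pilot.** Inputs: 20 patients and 3 months (synopsis), 4 per month (section 11.2), read as a whole-study rate as in SAP 6.4.4.

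- Recruited in the window: 4 × 3 = 12 of 20.
- Time to 20 patients: 20 / 4 = 5 months, 2 more than stated.
- Rate the window needs: 20 / 3 = 6.7 per month, 67% above the benchmark.
- If recruitment were a Poisson process with mean 4 per month (my assumption), the chance of reaching 20 within 3 months would be about 2%.

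**Main trial.** Inputs: 208 patients, or 208 − 20 = 188 if the pilot is pooled; 6 months.

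- Rate needed: 208 / 6 = 34.7 per month, or 188 / 6 = 31.3.
- To compare this with the benchmark I assume that each centre recruits 4 per month. The protocol does not say so. Months = patients / (4 × centres).

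| Centres | Patients per month | Months for 208 | Months for 188 | Per-centre rate for 208 in 6 months |
|---|---|---|---|---|
| 4 | 16 | 13.0 | 11.8 | 8.7 |
| 5 | 20 | 10.4 | 9.4 | 6.9 |
| 6 (pilot Trust plus 5 others) | 24 | 8.7 | 7.8 | 5.8 |
| 7 (two pilot sites counted separately, plus 5 others) | 28 | 7.4 | 6.7 | 5.0 |

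At 4 per month per recruiting unit, every row exceeds 6 months. If 4 per month were the rate for the whole main trial, 208 patients would take 208 / 4 = 52 months.

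**The case against.** The strongest reply concerns the unit. The protocol does not say whether 4 per month is per site or for the Trust. With two pilot sites, a per-site figure gives 8 per month and 20 / 8 = 2.5 months, inside the pilot window. If each of 5 main-trial centres also managed 8 per month, 208 / 40 = 5.2 months would fit as well. SAP 6.4.4 defines how the observed rate is calculated and never mentions 4 per month, so it does not settle what the protocol's authors meant. This much stands: the mismatch is shown on the SAP's whole-study definition and is not proved for every possible meaning. But neither document states the per-site meaning or a rate of 8 per centre. If per site was meant, the SAP's whole-study rate would be compared with a benchmark in another unit: a pilot recruiting 4 in total would pass at half the intended rate. The wording needs correcting either way.

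The main-trial durations are also an extrapolation from an estimate made at one Trust, for a trial that still depends on funding, the pilot results and an ethics amendment. That is fair, and it is why I give a range and state the assumption.

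Two stronger inferences are tempting and are not supported:

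- **That the decision to proceed rests on a wrong threshold.** Section 11.2 describes progression criteria in general as governing whether a main trial goes ahead. This trial's recruitment item, however, triggers only a revision of timelines, and the steering committee's red-amber-green review is there to decide which operational aspects to change. Nothing stops the committee from noticing that recruitment took 5 months.
- **That the main trial would be underpowered.** At 4 per centre, 4-5 centres would have 96-120 patients after 6 months. But neither document says recruitment closes at 6 months short of 208. Slow recruitment would lengthen the trial; it would not by itself reduce the sample.

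**Conclusion.** The point holds as an inconsistency between a planning benchmark and the timelines it is meant to protect. On the SAP's definition of the rate, the pilot part needs no further assumption: 5 months against 3, or 4 per month against 6.7. For the main trial, the required 34.7 per month (31.3 with pooling) follows directly from the plan. The durations of 10.4 to 13 months at 4-5 centres, or 8.7 months (7.8 for 188 patients) at 6, rest on the added assumption of 4 per centre per month. No single replacement duration can be fixed until the number of centres, the per-centre rate and the pooling of pilot patients are settled. The sample size, the analysis and participant safety are unaffected. It is worth correcting because the pilot is meant to inform exactly this planning.

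**What to change.** In protocol section 11.2, state the unit of the benchmark so that it matches SAP 6.4.4 (total across both pilot sites), and repeat the benchmark beside the SAP definition. Then take one of two routes:

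1. Set the benchmark at the rate the windows need: about 6.7 per month in total for the pilot, with a matching per-centre rate for the main trial (for 208 patients, 6.9 to 8.7 per month at 4-5 centres, or 5.8 at 6). The sponsor should then say why that is attainable, since its present estimate is 4.
2. Keep 4 per month, restate pilot recruitment as 5 months, and restate main-trial recruitment as the patients still to be recruited divided by the number of centres times the stated per-centre rate.

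Either route requires saying whether the 4-5 centres include the pilot Trust, and whether the target is 208 or 188 once pilot patients are counted. The cost is wording in the protocol synopsis, sections 6.1 and 11.2, and one line in the SAP, together with less favourable timelines or a more demanding benchmark.
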